Statistical methods	The primary endpoint and secondary endpoints will be evaluated using descriptive statistics. No confirmatory testing is performed and hence no null and alternative hypotheses are defined. All evaluations are to be considered exploratory.

FLOW CHART

Trial Periods	Screening	Treatment					End of study
Visit	1	2	3	4	5	6 / EoT ¹	7 / EoS ¹ / FU
Week	-6	0	1	4	8	12	16
Day	-42	1	8	29	57	85	113
Time window for visits [days]	≥7 d prior V2	-	±3	±3	±3	±3	+7
Informed consent ²	X						
Demographics	X						
Medical history / proof of CFB diagnosis	X	X					
CT scan (proof of BE diagnosis) ³	X						
Review of in-/ exclusion criteria	X	X					
Physical examination including skin	X	X	X	X	X	X	X
Vital signs, pulse rate, blood pressure, aural body temperature ⁵	X	X	X	X	X	X	X
Height (only at Visit 1) / body weight	X	X				X	
Sputum collection at site (spontaneous or induced) ⁶	X	X		X	X	X	X
Sputum collected at home (backup sample, if needed) ⁷		(X)		X	X	X	X
P. aeruginosa sputum sample for culture ⁸	X					X	
Murray sputum colour chart	X	X					
12-lead ECG	X	X		X		X	
Panoramic radiography ¹¹	X						
Safety laboratory tests (blood / urine samples) ¹²	X	X	X	X	X	X	(X)
Pregnancy tests ¹³	X	X		X	X	X	X
Cotinine (urine)	X	X		X	X	X	X
PK blood sample (profile) ¹⁵		X				X	
PK blood sample (trough) ¹⁵		X	X	X	X	X	

Trial Periods	Screening	Treatment						End of study
Visit	1	2	3	4	5	6 / EoT ¹		7 / EoS ¹ / FU
Week	-6	0	1	4	8	12		16
Day	-42	1	8	29	57	85		113
Time window for visits [days]	≥7 d prior V2	-	±3	±3	±3	±3		+7
[REDACTED]								
All AEs/SAEs/AESIs; concomitant therapy	X	X	X	X	X	X		X
Pulmonary exacerbation review, eCRF documentation		X	X	X	X	X		X
IRT call/notification	X ¹⁸	X		X	X	X		
Randomisation		X ¹⁹						
Dispense trial medication ²⁰		X		X	X			
Collect trial medication				X	X	X		
Compliance / drug accountability				X	X	X		
Completion of trial participant participation								X

- 1 Patients who completed treatment as planned will have an End of Treatment Visit (EOT) and a subsequent Follow up Visit after 28 (+7) days. The Follow-up Visit will be End of Study (EOS). Trial participants who discontinue trial treatment prematurely should undergo the EOT Visit as soon as possible and the EOS Visit 28 (+7) days thereafter.
- 2 Informed consent needs to be signed before any trial-related procedure is performed (before or at Visit 1).

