- 3 CT scan not older than 5 years at randomisation. A new CT may be performed for the purpose of the study, if the patient is otherwise eligible. It has to be ensured that local regulatory requirements regarding radiation exposure are fulfilled.

4 [REDACTED]

- 5 Measurements of vital signs should precede blood sampling and intake of trial medication.
- 6 Sputum samples will be used for NE activity and other biomarker assessment, details are provided in the ISF / lab manual.
- 7 All patients will be provided sputum containers for sputum collection at home in the morning of visit days, if possible. At V2 only applicable in case patient's eligibility providing sputum sample at site already confirmed (see [Section 5.4.1.3.2](#) for details).
- 8 *P. aeruginosa* culture from sputum samples will be performed at central lab.

9 [REDACTED]

10 [REDACTED]

Proprietary confidential information © 2023 Boehringer Ingelheim International GmbH or one or more of its affiliated companies

- 11 A standard panoramic radiograph is required for baseline assessment of the periodontal status at the dentist, historical radiographs taken within 1 year prior to randomisation are acceptable. If a new radiograph needs to be performed within the scope of the trial, this should happen if the patient is otherwise eligible and, if applicable, in accordance with local regulations regarding radiation exposure.
- 12 Laboratory tests for safety monitoring: HBV and HCV tests to be performed only at Visit 1, SARS-CoV-2 testing may be performed according to official local/national recommendations. At EOS, laboratory sample collection will be performed at the discretion of the investigator.
- 13 For WOCBP. At screening, a serum pregnancy test on β -HCG is performed. Urine dipstick pregnancy tests will be provided by central laboratory and should be performed at every visit (except at Visit 3).
- 14 [REDACTED]

(Note for Visit 1: fasting can only be asked for if informed consent was signed at least the day before V1)

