5.4.1.3.2 Sputum

Sputum collection at site

Sputum collection on visits indicated in the [Flow Chart](#) should occur with active breathing techniques, supported by the site staff, if needed. In case of difficulties producing sputum and no adequate sputum sample is produced spontaneously, induction of sputum is mandatory.

Recommendations for sputum induction will be provided in the ISF, however sites can also follow their own standards of saline inhalation or follow the standard operating procedure of the Cystic Fibrosis Therapeutics Development Network.

Sputum induction should only be performed after the pulmonary function test (details in [Section 6.2.2](#)).

If a sputum sample cannot be obtained on the day of the visit, it is generally possible that the patient returns the next day to provide the sputum sample.

To assess patient's eligibility for trial participation, at least one adequate sputum sample must be obtained at the site prior randomisation at V2 as indicated in the sputum decision tree for the screening period, [Figure 5.4.1.3.2: 1](#).

Sputum collection at home

After having confirmed patient's eligibility, the patient will be asked to collect spontaneous sputum accrued during the morning routine on visit days, if possible. This sample should be taken to the site in the provided collection containers and will serve as backup sample in case all attempts failed to obtain a sputum sample at site.

Sites will assess the quality of the backup sample macroscopically, including using the Murray Colour Chart.

A sputum decision tree for the treatment period is depicted in [Figure 5.4.1.3.2: 2](#). This approach is also applicable for a patient, who could provide a sputum sample at the site prior to Visit 2.

Detailed instructions on sampling, preparation, processing, shipment and storage are provided in the ISF / laboratory manual.

[figure not shown]

Figure 5.4.1.3.2: 1 Sputum decision tree – screening period V1 – V2 / eligibility

[figure not shown]

Figure 5.4.1.3.2: 2 Sputum decision tree – treatment period V4 – EOS; applicable for V2 only, if sputum sample already obtained at the site prior V2

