6.1 VISIT SCHEDULE

All patients are to adhere to the visit schedule as specified in the [Flow Chart](#). Each visit date (with its window) up to EOS is to be counted from Day 1 (Visit 2). If any visit has to be rescheduled, subsequent visits should follow the original visit date schedule. Additional visits for the purpose of re-testing of laboratory parameters or AE monitoring may be included as deemed necessary by the investigator. All deviations from the original schedule of visits and procedures will be documented and the implications considered for the analysis of the trial data.

[REDACTED]

[REDACTED] This applies also to the randomisation visit (V2).

Measurement of vital signs should precede blood sampling and be assessed pre-dose at all dosing visits.

If possible, blood sampling should always be performed at the same time of the day [REDACTED]

Patients should be instructed not to take the trial medication at home on scheduled visit days but bring it to the site and take it after pre-dose procedures were performed.

Procedures that should be performed pre-dose are [REDACTED] and safety assessment as AE and concomitant therapy collection, physical examination incl. vital signs and skin monitoring, ECG, and urine pregnancy test, if applicable. Also blood and urine sampling, incl. the pre-dose PK sample, should precede intake of study medication.

Sputum collection and pulmonary function test may be performed after intake of study medication, considering operational aspects and that no immediate effect on the lung is expected.

The order of the different trial procedures should be planned, taking into account the structure of the individual investigational site and following the requirements outlined in the clinical trial protocol and ISF/Lab Manual.

Visit days with full PK profile, i.e. V2 (randomisation visit) and EOT Visit, may be split over 2 consecutive days, i.e. procedures as [REDACTED] AE collection, physical examination and ECG could be completed the day before the main visit.

Preferred order of procedures during trial visits, where applicable:

1. [REDACTED])
2. **AE and concomitant therapy collection,** [REDACTED]
3. **Physical examination including vital signs and skin monitoring**
4. **ECG**
5. **Urine pregnancy test (if applicable)**
6. **Blood and Urine sampling, including trough (predose) PK sampling, safety lab and biomarkers**
7. **Sputum sample collection (if spontaneous)**

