## **6.7 BASELINE, TIME WINDOWS AND CALCULATED VISITS**

For all parameters (except for biomarkers), baseline is defined as the last non-missing value prior to first administration of trial medication, or on the same date of first drug administration, if assessment times are not collected (e.g., vital signs, laboratory tests).

For specific assessments, multiple measurements are planned prior to first drug intake (e.g., at Visit 1 or 2). To derive the baseline, specific rules will apply as shown in [Table 6.7: 1](#).

According to CTP Section 5.4.1.3.2 Sputum sample collection at site, if sputum samples do not meet the sputum collection criteria as defined in the ISF/Lab Manual, it is generally possible that the patient returns the next day to provide the sputum sample. Baseline sputum measurement could be on or prior to the first drug administration + 1 day.

Table 6.7: 1 Derivation of baseline for assessments with multiple measurements prior to first drug administration

Parameter	Baseline value derivation
Biomarkers based on sputum	Mean of all available valid measurements collected up to date of first study drug administration + 1 day
Murray sputum colour chart	Last valid measurement collected up to date of first study drug administration + 1 day
NEATstik®	Mean of all available valid samples collected up to date of first study drug administration + 1 day

Measurements taken after first administration of trial treatment will be considered either on- or off-treatment values based on the definition in [Table 6.1.1: 1](#). Visit windowing will be performed as described in the tables below, in order to assign data to the relevant study visit based on the actual day of the assessment. Data will be analyzed using the re-calculated visits in the statistical tables. However, in the listings, all visits performed will be displayed (even if outside time-window), along with the re-calculated visit. The date of first treatment intake will be used as Study Day 1 for the time windowing. If more than one value is available within one time window the one which is closest to the planned time/day is used for analysis. In case two values are equidistant from the planned time/day, then the last one will be picked.

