Analysis of AE data (including findings in 12-lead ECG assessments or physical examinations), potentially clinically significant abnormal laboratory values, concomitant medication or non-drug therapies will not be based on visits and thus no assignment to time windows is necessary. For this type of data, a safety analysis ‘on-treatment’ concept will be used depending on their actual onset dates.

Table 6.7: 2 Time windows for assignment of safety assessment – laboratory

[figure not shown]
Visit number (CTP)	Visit label (analysis)	Planned Day	Time window [days]		
			Window per CTP	Start (analysis)	End (analysis)
V1	Screening	-42	≥7d prior to V2	All pre-baseline measurements	
V2	Baseline	1	± 0	NA	Date/time of first administration of study drug
V3	Week 1	8	± 3	Start of on-treatment phase 	18
V4	Week 4	29	± 3	19	43
V5	Week 8	57	± 3	44	71
V6	Week 12	85	± 3	72	End of on-treatment phase 
EoS	Follow-up	113	+ 7	All post-treatment measurements after last drug intake + REP	

 As defined in [table 6.1.1: 1](#).

Table 6.7: 3 Time windows for assignment of biomarkers assessed in sputum

Visit number (CTP)	Visit label (analysis)	Planned Day	Time window [days]		
			Window per CTP	Start (analysis)	End (analysis)
V1	Screening	-42	≥7d prior to V2	All pre-baseline measurements	
V2	Baseline	1	± 0	NA	Date/time of first administration of study drug
V3	Week 1	8	± 3	Start of on-treatment phase 	18
V4	Week 4	29	± 3	19	43
V5	Week 8	57	± 3	44	71
V6	Week 12	85	± 3	72	Last drug administration
EoS	Safety Follow-up	Last drug administration + 28		All measurements after last drug administration + 1	All measurements before last drug administration + 36

 As defined in [table 6.1.1: 1](#).

Proprietary confidential information © 2024 Boehringer Ingelheim International GmbH or one or more of its affiliated companies.

For all variables with a sparse sampling schedule that does not match the schedules in the above tables, the screening, baseline and follow-up phase will follow the same rules, while the start and end days of the on-treatment time windows will be equidistant from the planned visit day.

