### **% inhibition analyses**

The assessment of NE activity will further comprise the analysis of the % inhibition of NE activity. For the purpose of descriptive analysis, for each time point including baseline, % inhibition will be calculated as:

$$NE \ inhibition_t = \frac{NE \ activity_{baseline} - NE \ activity_t}{NE \ activity_{baseline}} \times 100$$

Descriptive statistics for absolute % inhibition by timepoint and treatment group will be presented. Maximum % inhibition (on patient level during the trial) will be summarized by treatment group. The median % inhibition of NE activity per treatment group over time will be plotted. All timepoints will be taken into account, analysis windows will be applied to the % inhibition of NE activity.

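### The sputum window table has a Week 1 row for a visit with no sputum, and its baseline cut-off lets a post-dose Visit 2 sample count as both baseline and Week 1

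*SAP*

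**What the plan says.** **Schedule.** The protocol Flow Chart row "Sputum collection at site (spontaneous or induced" is marked at Visits 1, 2, 4, 5, 6 and 7. The row "Sputum collected at home (backup sample, if needed" is marked at Visit 2 (conditionally) and Visits 4 to 7. Visit 3 is blank in both. In protocol 5.4.1.3.2, the figure for treatment-period sputum is titled "Sputum decision tree – treatment period V4 – EOS; applicable for V2 only, if sputum sample already obtained at the site prior V2".

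**Timing within a visit.** Protocol 6.1 says "Sputum collection and pulmonary function test may be performed after intake of study medication", although its preferred order puts sputum before dosing. Protocol 5.4.1.3.2 lets a patient come back the next day if no sample is obtained.

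**Analysis windows (SAP 6.7).** "Table 6.7: 3 Time windows for assignment of biomarkers assessed in sputum" includes Visit 3, Week 1, planned Day 8, from the start of the on-treatment phase to Day 18. Its baseline row ends at the date/time of first dose.

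**Sputum baseline, three wordings:**
- Table 6.7: 1: "Mean of all available valid measurements collected up to date of first study drug administration + 1 day".
- Table 6.7: 3: up to the date/time of first dose.
- SAP 7.5.2.1: the mean of Screening and Week 0 before first intake.

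**Outputs (SAP 7.5.2.1).** NE is summarised by timepoint as log10 change and as % inhibition. Median % inhibition is plotted over time, and each patient's maximum is summarised. The section adds: "All timepoints will be taken into account, analysis windows will be applied to the % inhibition of NE activity".

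**The concern.** The on-treatment rows of the sputum table match those of the laboratory table (Table 6.7: 2), apart from the end of Week 12. Laboratory samples are taken at Visit 3 and sputum is not, so nothing planned can fill the Week 1 row. The only scheduled specimen that can land there is a Visit 2 sample taken after the first dose, and Table 6.7: 1 counts that same specimen as baseline.

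At stake is whether a reported Week 1 NE result means anything. It would not be a Day 8 measurement. It would come from patients whose sample happened to be taken late, and it would be measured against a mean that includes it. Protocol 1.2 reports that in healthy volunteers NE inhibition began only after 20 days of dosing, so an apparent Week 1 effect could mislead. The patient-level maximum is the most exposed output, because it keeps favourable chance values and discards unfavourable ones.

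**Working it through.** **1. Is the blank Flow Chart cell really Visit 3?** The pregnancy-test row has the same pattern of marks, and its footnote says the urine tests "should be performed at every visit (except at Visit 3". The gap is therefore Visit 3 and not an extraction fault.

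**2. Reproducing the plan's cut points.** They are midpoints of planned days, rounded down:
- (8 + 29)/2 = 18.5, giving 18/19
- (29 + 57)/2 = 43, giving 43/44
- (57 + 85)/2 = 71, giving 71/72

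All three match Table 6.7: 3. The first depends on Day 8, a visit without sputum.

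**3. Which scheduled samples fall between first dose and Day 18?** The ±3-day visit window and one extra day for next-day return are allowed.

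| Visit | Possible days | In the Week 1 window? |
|---|---|---|
| 2, after dosing | 1–2 | Yes |
| 4 | 26–33 | No |
| 5 | 54–61 | No |
| 6 | 82–89 | No |

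A Visit 4 sample would have to be 29 − 18 = 11 days early. Otherwise only unscheduled samples, or an early-discontinuation EOT sample taken close to the last dose, can enter.

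**4. How a post-dose Visit 2 sample is classified.** Table 6.7: 1 makes it baseline. Table 6.7: 3 puts it in Week 1. SAP 6.7 also says measurements after first administration are on- or off-treatment values. No precedence rule is stated.

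**5. What each reading gives.** Let V1 and V2 be the log10 values of one Visit 1 sample and one post-dose Visit 2 sample.

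| Reading | Baseline | Week 1 change (log10) |
|---|---|---|
| Baseline only | (V1 + V2)/2 | none |
| Both | (V1 + V2)/2 | V2 − (V1 + V2)/2 = (V2 − V1)/2 |
| On-treatment only (7.5.2.1 wording) | V1 | V2 − V1 |

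For % inhibition under the middle reading, let r be the ratio of the Visit 2 to the Visit 1 value on the raw scale. A raw-mean baseline gives (1 − r)/(1 + r) × 100. A log-mean baseline gives (1 − √r) × 100.

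| r | Raw mean | Log mean |
|---|---|---|
| 0.1 | 81.8% | 68.4% |
| 0.5 | 33.3% | 29.3% |
| 1 | 0% | 0% |
| 2 | −33.3% | −41.4% |
| 10 | −81.8% | −216.2% |

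**6. Sensitivity to an SD that the documents do not give.** Assume no drug effect and V2 − V1 normal with mean 0 and SD s. Inhibition of at least x then has probability Φ(2·log10(1 − x)/s) for a log-mean baseline and Φ(log10((1 − x)/(1 + x))/s) for a raw-mean baseline.

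| Assumed s (log10) | At least 50% | At least 80% |
|---|---|---|
| 0.5 | 11–17% | up to 3% |
| 1.0 | 27–32% | 8–17% |
| 2.15–2.48 | 39–42% | 26–35% |

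These are percentages of affected patients, not of all patients. The last row borrows the 2.15 from protocol 7.5; 2.48 is 2.15/√1.5 × √2, which treats 2.15 as the SD of a change from a two-sample mean.

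**The case against.** Several points on the other side stand.

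- **The Week 8 endpoint.** A reader might infer that the secondary endpoint is compromised. Its window is Days 44–71 with or without the Week 1 row. Only the choice between baseline wordings reaches the Week 8 change, and that is separate from the row. All analyses are descriptive and exploratory.
- **Precedence.** SAP 6.7 says specific rules apply to sputum baseline. If they override the window table, Visit 2 samples are baseline only and the row is almost empty. That is a reasonable reading, but the SAP does not state it and its on-/off-treatment sentence points the other way.
- **Frequency.** Post-dose sputum is a permitted exception, not the preferred order. How often it occurs cannot be known from the documents.
- **Large spurious inhibition.** The 26–35% figure is tempting to quote, but protocol 7.5 does not say what its SD of 2.15 measures. A one-sample normal calculation with n = 16 gives Φ((log10 0.2 − log10 0.1)/(2.15/4)) = 71% for the cell where the plan reports 64.7%, so the table does not settle the meaning. Applying that SD to two untreated samples is unsupported.
- **A change of exactly zero.** This needs the post-dose sample to be the only valid one. Protocol 5.4.1.3.2 requires an adequate site sample before randomisation, so it could happen only if that sample later proved invalid.
- **Early stoppers.** Sputum taken later than one day after the last dose meets the Safety Follow-up definition in the same table, so most early EOT samples go there.
- **Week 4.** The start at Day 19 loses no scheduled sample. The SAP's equidistance rule covers variables that do not match the tables, so a Day 15 start would be an analogy, not a requirement.

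**Conclusion.** The point holds as a contradiction within the SAP's derivation rules. The sputum table provides for a visit with no sputum, and three baseline wordings leave a post-dose Visit 2 sample with no single classification. Followed literally, Tables 6.7: 1 and 6.7: 3 use the same specimen on both sides of a change from baseline. This is a conflict between written rules, not merely missing detail.

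For one Visit 1 and one post-dose Visit 2 sample with a log-mean baseline, the artefact is exactly half the difference between them. Its distribution cannot be fixed from the documents. The range in the sensitivity table is wide, and it applies only to an unknown number of patients.

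The exposure is confined to the by-timepoint NE summaries, the median % inhibition plot and the patient-level maximum. The documents do not support extending it to the Week 8 window or to the scheduled Week 4 samples. It is worth correcting because these outputs describe a secondary-endpoint biomarker and the correction is small.

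**What to change.** Before unblinding:

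1. Delete the Visit 3/Week 1 row from Table 6.7: 3.
2. End sputum baseline at the date of first dose plus one day in Table 6.7: 1, Table 6.7: 3 and SAP 7.5.2.1 alike.
3. State that a sample used for baseline is never also an on-treatment value, including for the maximum % inhibition.
4. List, without assigning to a visit, any unscheduled sputum between the end of baseline and the start of the Week 4 window. That start may stay at Day 19 or be reset.

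The cost is one table edit and two sentences in the SAP. The downside is that a few unscheduled early samples would appear only in a listing, so the statement that all timepoints are taken into account needs a matching qualification.

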## **7. PLANNED ANALYSIS**

The labelling and display format of statistical parameters will follow BI standards (9.7). For End-Of-Text (EoT) tables, the set of summary statistics is: N / Mean / SD / Min / Median / Max. In descriptive statistics tables, mean, SD and median will be rounded to one additional digit than the raw individual value. In case extreme data outside of the expected range are observed, quartiles and percentiles will be presented additionally.

Tabulations of frequencies for categorical data will include all possible categories and will display the number of observations in a category as well as the percentage (%) relative to the respective treatment group (unless otherwise specified, all subjects in the respective subject set whether they have non-missing values or not). The category missing will be displayed only if there are actually missing values.

